13.11.2. Setting

The study will be based within three NHS PICUs:

- University Hospital Southampton NHS Foundation Trust (Southampton Children's Hospital).
- King's College Hospital NHS Foundation Trust, London.
- Birmingham Women & Children's NHS Foundation Trust.

13.11.3. Population and sampling

- **PERMIT champions:** To prepare for implementing the PERMIT intervention, each PICU forms a group of PERMIT champions (i.e. lead multidisciplinary health care professionals and managers). These individuals will help shape and promote all aspects of ERM implementation across steps 1-3 of the study. Throughout the study, we will conduct a weekly debrief with 6-15 champions (2-5 per PICU).
- **PICU health care professionals:** The PERMIT intervention will be delivered to CYP by multidisciplinary health care professionals working within each PICU. This includes doctors, nurses and allied health professionals (e.g. physiotherapists, occupational therapists, speech and language therapists, play therapists, psychologists etc). The PICU health care professionals group could include the PERMIT champions described above. At steps 1, 2 and 3 of the study, we will conduct a brief online survey of at least 30 health care professionals per survey (10 per PICU, per survey). In other words, we will conduct a total of three surveys involving a total of 90 health care professionals. For step 3 of the study, which focuses on outcomes and impact, we will also conduct interviews with 12-15 of the health care professionals (4-5 per PICU).
- **Children and young people (CYP):** Step 2 of the study focuses on delivering the PERMIT intervention to CYP and monitoring delivery, safety and adverse events. We aim to recruit 30 CYP in total to receive the intervention (10 per PICU). We will include CYP (aged 0 to <16 years) admitted to PICU for any reason and who are likely to remain within PICU on day 3 post-admission. We will obtain consent to receive the PERMIT intervention from a parent/legal guardian and assent from the CYP where possible. We will exclude patients where the local clinical team do not feel it is appropriate to include them in the study for whatever reason.
- **Parents/legal guardians of CYP receiving the PERMIT intervention:** Step 3 of the study focuses on measuring outcomes and assessing the impact and acceptability of the PERMIT intervention. Parents/legal guardians of the CYP included in step 2 (i.e. 30 parents/legal guardians in total, 10 per PICU) will be approached and consented to complete outcome

measurement tools and an interview. We will also conduct interviews with 12-15 of the consenting parents/legal guardians (4-5 per PICU).

- **Parents/legal guardians who decline for their child to receive the PERMIT intervention:** At step 2 of the study, we anticipate that some parents/legal guardians of CYP fulfilling the eligibility criteria will choose not to provide consent for their child to receive the PERMIT intervention. Instead, their child will receive 'usual' PICU ERM. This group are often excluded from providing information about future trial feasibility, however their views are extremely important. For step 3 of the study, we will invite these parents/legal guardians to participate in an interview to discuss their decision making and views of ERM. We will aim to interview 3 parents/legal guardians in total (1 per PICU).

13.11.4. Screening, recruitment and consent

All screening, recruitment and consent will be managed by the Local and Central PERMIT Research Teams:

- **Local PERMIT Research Team:** Each of the three participating PICU sites will identify a Principal Investigator, supported by a therapist/nurse. This will form the Local PERMIT Research Team, who will provide local data collection at the sites.
- **Central PERMIT Research Team:** The Chief Investigator and the PERMIT Trial Management Group will form the Central PERMIT Research Team and provide support, oversight and centralised data collection across the sites.

We require agreement and consent at a PICU level to prepare the PICU for implementing the PERMIT intervention (step 1) and to deliver the PERMIT intervention to CYP (step 2). PICU-level consent will be provided by the Clinical Lead during the local R&D trial approval process for the PERMIT feasibility study. This provides consent for the unit to engage in implementing the PERMIT intervention and follow the specified implementation process in the PERMIT intervention manual.

PICU-level approval will also provide permission for the Local PERMIT Research Team to approach PERMIT champions for the weekly debrief and PICU health care professionals for the three brief online surveys, as described below.

13.11.5. Step 1:

Step 1 will assess the feasibility of implementing the preparation phases of the PERMIT intervention in the three PICUs (i.e. phase 1 'build the team', phase 2 'take stock', phase 3 'get buy-in' and phase 4 'get ready').

PERMIT champions: Following REC and local R&D approval, the Local PERMIT Research Team at each site will share the protocol and the PERMIT intervention manual (PERMIT-Intervention-Manual-V1_09.12.2020) with the medical, nursing and therapy leads within their PICU to nominate and 'build the team' of PERMIT champions. The Local PERMIT Research Team will provide the PERMIT champions with an email invitation (PERMIT_Champion_Weekly_Debrief_Email_Invitation_V1_07.12.2020), participant information sheet (PERMIT_Champion_Debrief_Participant_Information_Sheet_V1_07.12.2020), and consent form (PERMIT_Champion_Debrief_Consent_Form_V1_07.12.2020) regarding taking part in the weekly debrief. Consent forms will be completed with a member of the Local PERMIT research team.

PICU health care professionals: The Local PERMIT Research Team at each site will use internal email lists to invite all multidisciplinary PICU health care professionals to complete the first brief online survey. They will send an email invitation (PERMIT_Health_Care_Professional_Survey_Email_Invitation_V1_07.12.2020) after the health care professionals have received education about the PERMIT intervention from the PERMIT champions,

17/21/06: The PERMIT Feasibility Study

but before any patient recruitment starts. The email invitation will have a participant information sheet (PERMIT_Health_Care_Professional_Survey_Participant_Information_Sheet_V1_07.12.2020) attached. Both these documents highlight that completion and submission of the survey is an indicator of informed consent. Therefore, no separate consent form will be required.

Completed surveys are automatically submitted to the Central PERMIT Research Team for processing and analysis. The Central PERMIT Research Team will monitor survey responses to ensure that relevant health care professional groups and the three PICUs are represented. If required, the Local PERMIT Research Team at each site will send the email invitation again to specific under-represented groups. This will ensure that we have representatives from all three units, from different health care professional groups and from people who have had a variety of experiences.

13.11.6. Step 2:

After phases 1-4 have been satisfactorily implemented, study sites will progress to step 2. Step 2 will assess the feasibility of implementing the delivery phases of the PERMIT intervention (i.e. phase 5 'make it work' and phase 6 'keep it going').

PERMIT champions: The weekly debrief with consenting PERMIT champions will continue.

PICU health care professionals: The Local PERMIT Research Team at each site will invite all multidisciplinary PICU health care professionals to complete the second brief online survey, following the same process as described for step 1.

CYP: We will display a poster (PERMIT_Recruitment_Poster_V1_07.12.2020) about the PERMIT feasibility study in public areas in each PICU. Basic information about the study, in the form of an awareness leaflet (PERMIT_Awareness_Leaflet_V1_07.12.2020), will be provided to all parents/legal guardians of CYP admitted to PICU during the study period.

In conjunction with patient's clinical team, the local PERMIT Research Team will screen and recruit CYP to receive the PERMIT intervention. They will screen all CYP admitted to each PICU against the study inclusion and exclusion criteria and record the screening and all related decisions in the screening log at each site. They will approach the parents/legal guardians of eligible CYP on day 1 or 2 of admission (where possible). They will explain the study and provide the participant information sheet (PERMIT_Parent_Legal_Guardian_Participant_Information_Sheet_A_V1_07.12.2020).

After providing time for parents/legal guardians to read the information and consider the study, the Local PERMIT Research Team will return to ask for consent for the CYP to take part in the study using the consent form (PERMIT_Parent_Legal_Guardian_Consent_Form_A_V1_07.12.2020). They will discuss the different options for consent. At this point, parents/legal guardians can choose between the following:

- Consenting for CYP to receive the PERMIT intervention, with accompanying data collection (specifically, CYP clinical data, PERMIT intervention data and safety monitoring). No additional requirements for parents/legal guardians.
- If they consent to the PERMIT intervention, they can also consent to complete additional outcome measurement tools (e.g. related to quality of life, fatigue, pain).
- If they consent to the PERMIT intervention and complete additional outcome measurement tools, they can also consent to an optional interview to assess acceptability.

Consent from parents/legal guardians will be obtained by a member of the Local PERMIT Research Team, with copies provided to the parents/ legal guardians and for the medical notes.

We will obtain consent to receive the PERMIT intervention from a parent/legal guardian and assent from the CYP where possible at the time of recruitment.

17/21/06: The PERMIT Feasibility Study

The majority of CYP will be unable to provide assent to participate (for example; because of their age (<1 year of age), on pain relief medications, sedated to tolerate interventions). Therefore, we will rely primarily on consent from parents/legal guardians. However, where possible and appropriate, the Local PERMIT Research Team will seek verbal or written assent from the CYP themselves at the time of recruitment. Where this was not possible and consent has already been obtained from their parent/legal guardian, the research team will approach at a later date to discuss the study and gain assent. Assent will be recorded on CYP assent form PERMIT_Child_Assent_Form_V1_07.12.2020), which will be completed with a member of the Local PERMIT Research Team with copies provided to parents/legal guardians and for the medical notes. During the assenting process, the Local PERMIT Research Team will ensure that CYP:

- Understand the purpose and nature of the research.
- Understand what the research involves, its benefits, risks and burdens.
- Understand the alternatives to taking part.
- Are able to retain the information long enough to make an effective decision.
- Are able to make a free choice.
- Are capable of making this particular decision at the time it needs to be made (recognising that their capacity may fluctuate, and they may be capable of making some decisions but not others depending on their complexity).

The Local PERMIT Research Team will employ a 'best interests' approach. Mental capacity will be assumed unless proven otherwise. All members of the Local PERMIT Research Team recruiting CYP into this study will have been trained in Mental Capacity Assessment as part of routine clinical training.

Parents/legal guardians and CYP may request withdrawal from the PERMIT feasibility study at any point, including during step 2 where they have agreed for their child to receive the PERMIT intervention. Reasons for withdrawal will be recorded in the screening logs at each PICU site. At the time of withdrawal we will ascertain if they wish to withdraw from ongoing involvement in the PERMIT intervention or if they wish for all their previously collected data to be removed.

13.11.7. Step 3:

PERMIT champions: The weekly debrief with consenting PERMIT champions will continue.

PICU health care professionals: The Local PERMIT Research Team at each site will invite all multidisciplinary PICU health care professionals to complete the third and final brief online survey, following the same process as described for steps 1-2.

At the end of each of the three brief online surveys, health care professionals will be asked if they would be willing to consider taking part in an interview. If they indicate yes, they will be asked to provide their name and email address. Their name and email address will not be linked to any of their survey responses. Completed surveys – and any names and email addresses provided – are automatically submitted to the Central PERMIT Research Team for processing and analysis.

To recruit health care professionals for the interviews, we will use two approaches: (i) the Central PERMIT Research Team will send an email invitation (PERMIT_Health_Care_Professional_Interview_Email_Invitation_V1_07.12.2020) to survey respondents who agreed to consider taking part in an interview, and (ii) the Local PERMIT Research Team will send the same email invitation asking for participants from specific under-represented groups or groups that we are particularly keen to hear from. This two-pronged approach will ensure that we have representatives in the interviews from all three units, from different health care

17/21/06: The PERMIT Feasibility Study

professional groups and from people who have had a variety of experiences of the PERMIT intervention.

The Participant Information Sheet

(PERMIT_Health_Care_Professional_Interview_Participant_Information_Sheet_V1_07.12.2020) and consent form (PERMIT_Health_Care_Professional_Interview_Consent_Form_V1_07.12.2020) will be sent by email to the potential participant by the researcher from the Central PERMIT Research Team. Participants will be asked to complete and return the consent form via email to a secure nhs.net address. Prior to commencing the interview the participant information sheet will be discussed and consent re-affirmed verbally.

Health care professionals responses to the on line survey cannot be withdrawn as they are anonymous. Health care professionals may withdraw their consent to participate during or after an interview. We will ask permission to use any information already provided. If participants do not provide this permission, we will remove all data.

CYP: Throughout step 3, the Local PERMIT Research Team will continue to screen and recruit CYP to receive the PERMIT intervention, as described in step 2.

Parents/legal guardians of CYP receiving the PERMIT intervention: The Local PERMIT Research Team will re-approach parents/legal guardians of the CYP included in step 2 who also agreed to complete additional outcome measurement tools (e.g. related to quality of life, fatigue, pain) and may also have agreed to take part in an interview to assess acceptability. The Local PERMIT Research Team will reaffirm their consent and support parents/legal guardians to complete the outcome measurement tools. To facilitate arranging the interviews, the Local PERMIT Research Team will share the completed consent forms (which also consent to consider an interview) via nhs.net email with the relevant researchers from the Central PERMIT Research Team who will be conducting the interviews, along with the parent/legal guardian contact details. Contact details for individual parents/legal guardians will be shared only with the individual researcher who will be conducting that particular interview.

The Local PERMIT Research Team will re-approach parents/legal guardians of the CYP included in step 2 who **only** agreed only for their child to receive the PERMIT intervention with accompanying data collection. The Local PERMIT Research Team will use a participant information sheet (PERMIT_Parent_Legal_Guardian_Participant_Information_Sheet_B_V1_07.12.2020) and consent form (PERMIT_Parent_Legal_Guardian_Consent_Form_B_V1_07.12.2020) to ask for parent/legal guardian consent to participate in completing the additional outcome measurement tools and an interview. This re-approach to parents/legal guardians will take place during their PICU admission and up to 30 days post-admission. Consent will be obtained by the Local PERMIT Research Team. To facilitate arranging the interviews, the Local PERMIT Research Team will share the completed consent forms with the Central PERMIT Research Team, as described above.

Parents/legal guardians and CYP may request withdrawal from the outcome assessments. Reasons for withdrawal from the outcome questionnaires will be recorded. We will ascertain if they wish to withdraw from ongoing questionnaire completion alone or if they wish for all their previously collected data to be removed. Parents/legal guardians may also withdraw their consent to participate during or after an interview. We will ask permission to use any information already provided. If participants do not provide this permission, we will remove all data.

Parents/ legal guardians of CYP who decline for their child to receive the PERMIT intervention: The Local PERMIT Research Team will approach parents/legal guardians who declined at step 2 for their child to receive the PERMIT intervention. They will provide a participant information sheet (PERMIT_Parent_Legal_Guardian_Participant_Information_Sheet_C_V1_07.12.2020) regarding

taking part in an interview. They will approach these parents/legal guardians during their PICU admission or up to 30 days post-admission. Consent will be obtained by the Local PERMIT Research Team using a consent form (PERMIT_Parent_Legal_Guardian_Consent_Form_C_V1_07.12.2020). To facilitate arranging the interviews, the Local PERMIT Research Team will share the completed consent forms with the Central PERMIT Research Team, as described above. Parents/legal guardians may also withdraw their consent to participate during or after an interview. We will ask permission to use any information already provided. If participants do not provide this permission, we will remove all data.

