13.12.2. Secondary outcomes

[figure not shown]
- **Acceptability of all data collection forms, outcome measurement tools and the PERMIT intervention as a whole:**
 - We will use the weekly debrief with PERMIT champions, interviews with PICU health care professionals and interviews with parents/legal guardians to assess acceptability of all data collection forms, outcome measurement tools and the PERMIT intervention as a whole. These data, along with the data from the data collection forms and outcome measurement tools themselves, will also provide us with an indication of the potential impact of the PERMIT intervention on CYP and parents/legal guardians.
 - **Number of ERM activities prescribed per CYP following patient acuity screening:**
 - The Local PERMIT Research Team will record the number of ERM activities prescribed to CYP follow daily acuity screening daily.
 - **Number of ERM activities delivered per CYP:**
 - The Local PERMIT Research Team will convert prescribed ERM activity to delivered ERM activity and will calculate this on a daily basis.
 - **Safety and adverse event rates during an ERM activity:**
-

17/21/06: The PERMIT Feasibility Study

- The Local PERMIT Research Team will undertake safety and adverse event reporting by day, by patient and by PICU.
- **Safety and adverse event rates throughout the whole PERMIT intervention study period:**
 - The Local PERMIT Research Team will undertake safety and adverse event reporting by day, by patient and by PICU.

17/21/06: The PERMIT Feasibility Study

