At point of PICU discharge or within 30 days post admission to PICU. Parents/legal guardians will report based on their child's current status by completing: (1) Pediatric Quality of Life Inventory (PedsQL)™ Infant Scales Version 4.0 – Acute (Aged: 1-23 months) OR PedsQL™ Generic Core Scales Version 4.0 - Acute (Aged: 2 years+); and (2) PedsQL™ Multi-dimensional Fatigue Scale Version 3.0 - Acute; and (3) The PedsQL™ Pediatric Pain Questionnaire (PPQ)™ will also be completed at this second time point.

13.13.8. Parent/legal guardian outcome measurement tools:

The Local PERMIT Research Team will collect the following data from parents/legal guardians using validated outcome measurement tools (see Appendix 1). The outcome measurement tools will be administered via the preferred communication methods of the parent/legal guardian e.g. face to face, telephone, videoconference, or paper-based or electronic. The information will be entered into the PERMIT study RedCAP database.

Parent/legal guardian outcomes will be measured at two time points:

During PICU admission. Parents/legal guardians will provide a retrospective report based on their own and families pre-admission status (two weeks before) by completing: (1) Parents/legal guardians will report based on their child's current status by completing: (1)The PedsQL™ Family Impact Module Version 2.0;

At point of PICU discharge or within 30 days post admission to PICU. Parents/legal guardians will report based on their child's current status by completing: (1)The PedsQL™ Family Impact Module Version 2.0; (2) Parent Stressor Scale: PICU; (3) The EMpowerment of PArEnts in The Intensive Care - 30 Item Version (EMPATHIC-30); and (4) Patient Health Questionnaire-4 (PHQ-4).

Interviews with parents/legal guardians of CYP receiving the PERMIT intervention

The Central PERMIT Research Team will conduct interviews with these parents/legal guardians to assess the acceptability of the PERMIT intervention, related data collection and outcome measurement tools and future trial designs. The interviews will be conducted towards the end of the

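### For parents of treated children, the listed consent options tie the acceptability interview to the outcome questionnaires, so those who refuse the questionnaires have no stated way to explain why in an interview

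*Protocol*

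**What the plan says.** Section 13.11.6 sets out what a parent may choose on Form A:

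- Intervention only: "Consenting for CYP to receive the PERMIT intervention, with accompanying data collection".
- Questionnaires added: "If they consent to the PERMIT intervention, they can also consent to complete additional outcome measurement tools".
- Interview added: "If they consent to the PERMIT intervention and complete additional outcome measurement tools, they can also consent to an optional interview to assess acceptability".

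Section 13.11.7 describes a second approach, on Form B, to parents who "agreed only for their child to receive the PERMIT intervention with accompanying data collection". Its purpose is "to ask for parent/legal guardian consent to participate in completing the additional outcome measurement tools and an interview". Section 13.11.3 pairs questionnaires and interview in the same way for the parents of all 30 treated children, and plans 12-15 interviews among those who consent.

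Section 13.12.2 lists the secondary outcome "Acceptability of all data collection forms, outcome measurement tools and the PERMIT intervention as a whole". Its sources are the champion debriefs, the staff interviews, the parent interviews, and the data from the forms and tools themselves. Section 13.13.8 gives the aim of the interviews with parents of treated children as "to assess the acceptability of the PERMIT intervention, related data collection and outcome measurement tools and future trial designs".

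Parents who decline the intervention have their own route on Form C, with three interviews planned and no questionnaire condition (13.11.3, 13.11.7, 13.13.9). Of these parents the protocol says: "This group are often excluded from providing information about future trial feasibility, however their views are extremely important".

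**The concern.** Among parents of treated children, the wording makes access to the interview depend on a behaviour that the interview is partly meant to explain. Step 3 asks whether outcomes can be measured, completion of the outcome tools is a primary outcome (13.12.1), and the analysis section promises to report obstacles to collecting the outcome measures (13.20.3). The parents who can best describe such an obstacle are those who accepted the intervention and turned the questionnaires down. The parental view of the questionnaires would then come from a group selected for having agreed to them. The protocol recognises the value of decliners' views, but provides an interview route only for those who decline the intervention itself.

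**Working it through.** The point rests on the consent structure, and the protocol states no figure to reproduce. The check is to follow each type of parent through the listed routes.

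| Parent | Stated route to an interview | Questionnaires among the stated interview topics? |
|---|---|---|
| Accepts intervention and questionnaires (Form A) | Yes (13.11.6) | Yes (13.13.8) |
| Intervention only at first, then accepts both on Form B | Yes (13.11.7) | Yes |
| Agrees to the questionnaires, later stops them | Not stated to be removed (13.11.7) | Yes |
| Accepts intervention, refuses the questionnaires both times | None stated | Not applicable |
| Declines intervention (Form C) | Yes, 3 planned | No: decision making, views of early rehabilitation, trial designs (13.13.9) |

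Only the fourth row is left without a stated route.

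**Is refusing the questionnaires alone plausible?** From the item counts in 13.13.10, for a child aged 2 years or over, using the longer 23-item form:

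- Completed twice: 2 x (23 + 18 + 36) = 154 items.
- Completed once: 1 + 30 + 30 + 4 = 65 items.
- Total: 154 + 65 = 219 items.
- Time, taking each listed limit: 2 x (5 + 5 + 5) + 1 + 10 + 15 + 2 = 58 minutes at most.

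The interview is put at about 30-40 minutes in the text (13.13.8) and at up to 60 minutes in the table. A parent could reasonably accept a conversation and not the forms.

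**How many parents could be affected?** Questionnaire uptake is not given, so the uptake values below are assumptions. They count parents who agree at either approach, with one parent per child and the full 30 recruited. Interview pool = 30 x uptake; without a stated route = 30 - pool.

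| Assumed uptake | Interview pool | No stated route |
|---|---|---|
| 100% | 30 | 0 |
| 80% | 24 | 6 |
| 60% | 18 | 12 |
| 50% | 15 | 15 |
| 40% | 12 | 18 |

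The lower interview target of 12 needs uptake of at least 12/30 = 40%, even if every parent in the pool agrees to be interviewed. The upper target of 15 needs 15/30 = 50%. If the questionnaires prove burdensome, the nesting therefore also puts the interview sample at risk.

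**The case against.** The strongest reply is that the gap is read into forms that are not in the documents. In the Form B wording, the joint request may list two separate choices. Section 13.13.8 defines the interviewees as parents of children receiving the intervention, with no questionnaire condition, and a single interview schedule serves Forms A and B. Consent graded by burden is also a recognisable choice for parents approached on day 1 or 2 of admission. This reply stands so far as it goes: the forms may already allow a separate choice. But the Form A options in 13.11.6 are explicit, and 13.11.7 does not undo them.

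A reader might infer more than the protocol supports, in four ways:

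- That questionnaire acceptability is judged only by parents who agreed to the questionnaires. Champion debriefs, staff interviews and the tool data also contribute (13.12.2).
- That there would be no parental information on low completion. Reasons for withdrawing from the questionnaires are recorded, and nothing bars those parents from interview (13.11.7).
- That acceptability must look favourable whatever the refusal rate. The primary completion outcome is worded for eligible children (13.12.1), so on that wording refusal lowers the reported figure and is visible.
- That views on future trial design come only from questionnaire-takers. The three parents who declined the intervention are asked about it too (13.13.9).

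None of these supplies the first-hand account of a parent who took the intervention and never agreed to the questionnaires. Staff accounts are second-hand, withdrawal reasons concern people who had first agreed, and the three Form C parents refused something else.

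**Conclusion.** The point holds in a limited form. For parents of treated children, 13.11.6 makes the interview conditional on the questionnaires, and 13.11.3 and 13.11.7 do not clearly separate the two. Parents who persistently refuse the questionnaires have no stated route to the interview intended to assess, among other things, how acceptable the questionnaires are. This is a selection effect on one source of a secondary outcome and a gap in the reporting of obstacles to outcome measurement. It does not invalidate step 3.

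Its size depends on unknown uptake: 6 to 15 of 30 families at an assumed 80% to 50%, and none if every family agrees. The conclusion rests on the protocol text, since Forms A and B are not shown. If the forms already offer the interview separately, the protocol should say so.

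**What to change.** In 13.11.3, 13.11.6 and 13.11.7, and in consent forms and information sheets A and B, state that a parent of a treated child may accept the interview without the outcome questionnaires. Within the planned 12-15 interviews, purposively include parents who declined or did not complete the questionnaires, where any are available and willing.

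A fixed quota per unit is not needed. It might be impossible to fill if few parents refuse the questionnaires or if those who do also refuse an interview. Separate reporting for perhaps three such parents would add little to a qualitative sample of this size.

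The cost is a small amendment to the protocol wording, forms and information sheets, with no extra interviews. The downside is slightly fewer interviews with parents who completed the questionnaires.
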